4.5.4.2.1 Pre-treatment evaluations (up to 4 weeks: -28 to Day -1)

The following procedures will be performed at the pre-treatment visit of **Part B** as reported below:

- Informed consent signing;
- Demographic data (race, sex and date of birth);
- Adverse event recording;
- Concomitant medications (drugs);
- Significant non-drug therapies (e.g. phlebotomies, transfusions) recording (*if applicable*);
- Medical history;
- Physical examination, vital signs (blood pressure, pulse rate, respiratory rate), height, weight, body temperature and ECOG performance status;
- Pregnancy test (*if indicated*);
- Blood chemistry: ALT/SGPT, AST/SGOT, ALP, total bilirubin, LDH, creatinine, BUN or Urea (as per site-specific clinical practice; see [Appendix F](#) to convert Urea to BUN), glucose, Na, K, Ca, Cl, Mg, albumin, eGFR determination (according with the Mayo Clinic Quadratic Equation);
- ECG, QTc determination (according with Bazett's correction formula);
- Urinalysis: pH, specific gravity, protein, glucose;
- Haematology: RBC count, HCT, Hb, MCV, MCH, MCHC, WBC count (full and differential), PLT count;
- Spleen evaluation by MRI or CT scan;
- Collection of a blood sample for the quantitative RT-PCR evaluation of JAK2^{V617F} mutational status on peripheral blood (PB) granulocyte;
- Assessment of disease-related symptoms using the MPN-SAF QOL Questionnaire [24, 32];
- Bone marrow histological evaluation, in patients who have consented to this optional exploratory research, who haven't this assessment in the month before the 1 month before the study start (i.e the signature of the Informed Consent

Form, and that have not any medical contraindication to bone marrow sampling as judged by the Investigator);

- Request of enrolment and receipt of patient ID.

Patients must have an Eastern Cooperative Oncology Group (ECOG) performance status [28] ≤ 2 within 7 days of initiating study drug.

The pregnancy test (if indicated) has to be performed within 72 hours before the first Givinostat dose. The test can be performed by urine or serum pregnancy test. In case of a borderline-positive urine pregnancy test, this must be confirmed with a serum pregnancy test and the result recorded in the CRF. Pre-treatment evaluations will be performed at one or more clinic visit to determine eligibility for the study. Pre-treatment evaluations must be performed up to 4 weeks before the treatment start within ± 7 days.

Please note that, in case the patient performs the bone marrow histological evaluation as requested by the “new” ELN criteria (i.e. the **revised** ELN response criteria) [33] (see [paragraph 4.8.7](#)) – i.e. bone marrow evolution including the assessment of the presence of age adjusted normocellularity and/or trilinear hyperplasia - 1 month before the study start (i.e. the signature of the Informed Consent Form), this examination has not to be repeated for this study in order to limit the discomfort for the patient. In any case, the results of this test will be transcribed into the CRF and the original signed and dated laboratory print-out/tracings, including the assessment of the presence of age adjusted normocellularity and/or trilinear hyperplasia, will be monitored and stored at the study site.

In case the patient refuses to provide this written consent to perform the bone marrow evaluation, this patient can be anyway recruited in **Part B**. However, this patient will not be counted to assess the related exploratory endpoints (i.e. overall response rate of Givinostat at the MTD after 6 cycles according to the revised ELN response criteria [33], and the evaluation of the effect of Givinostat on each single response parameter according to the revised ELN response criteria [33]).

If all eligibility criteria are met at the pre-treatment visit, the treatment with Givinostat can start.

After the check that all eligibility criteria are met by the patient and in any case before the treatment start, all patients with an uncontrolled HCT (i.e. HCT $\geq 45\%$) have to perform phlebotomy(ies) to normalize the HCT value (i.e. HCT $<45\%$).

In case of patients who are phlebotomy-dependent, all efforts have to be made by Investigators to record all phlebotomies with recruited patients experienced at least 6 months before the treatment start.

4.5.4.2.2 Day 1 of Cycle 1

The following procedures must be performed exactly at Day 1 of Cycle 1 of **Part B** as reported below:

1) Pre-dose evaluations:

The following procedures will be performed **before the first Givinostat dose** as reported below:

- Adverse event recording;
- Concomitant medications (drugs);
- Significant non-drug therapies (e.g. phlebotomies, transfusions) recording (*if applicable*);
- PD sample collection;
- PK sample collection and preparation, in order to allow to perform both the PK and PD evaluations starting from the same sample [34] (*if requested*).

2) Post-dose evaluations:

The following procedures will be performed **after the first Givinostat dose** as reported below:

- Adverse event recording;
- Concomitant medications (drugs);
- Significant non-drug therapies (e.g. phlebotomies, transfusions) recording (*if applicable*);
- PD sample collection **12 hours after the first Givinostat dose**;
- PK sample collection (2, 3 and 8 hours post-dose) and preparation, in order to allow to perform both the PK and PD evaluations starting from the same sample [34] (*if requested*);
- First Givinostat dose and accountability.

4.5.4.2.3 Day 28 of Cycles 1, 2, 4 and 5

The following procedures will be performed at Day 28 of Cycles 1, 2, 4 and 5 of **Part B** (within ± 3 days) as reported below:

- Adverse event recording;
- Concomitant medications (drugs);
- Significant non-drug therapies (e.g. phlebotomies, transfusions) recording (*if applicable*);

- Physical examination, vital signs (blood pressure, pulse rate, respiratory rate), weight, body temperature and ECOG performance status;
- Blood chemistry: ALT/SGPT, AST/SGOT, ALP, total bilirubin, LDH, creatinine, BUN or Urea (as per site-specific clinical practice; see [Appendix F](#) to convert Urea to BUN), glucose, Na, K, Ca, Cl, Mg, albumin, eGFR determination (according with the Mayo Clinic Quadratic Equation);
- ECG, QTc determination (according with Bazett's correction formula);
- Haematology: RBC count, HCT, Hb, MCV, MCH, MCHC, WBC count (full and differential), PLT count;
- Collection of a blood sample for the quantitative RT-PCR evaluation of JAK2^{V617F} mutational status on peripheral blood (PB) granulocyte;
- Used/unused/partially used Givinostat supply return, Givinostat administration and Givinostat accountability;
- **Only at Cycle 2:** PK sample collection (pre-dose and 1, 2, 4 and 8 hours post-dose) and preparation, in order to allow to perform both the PK and PD evaluations starting from the same sample [34] (*if requested*).

4.5.4.2.4 Day 28 of Cycles 3 and 6

The following procedures will be performed at Day 28 of Cycles 3 and 6 of **Part B** (within ± 3 days) as reported below:

- Adverse event recording;
- Concomitant medications (drugs);
- Significant non-drug therapies (e.g. phlebotomies, transfusions) recording (*if applicable*);
- Physical examination, vital signs (blood pressure, pulse rate, respiratory rate), weight, body temperature and ECOG performance status;
- Blood chemistry: ALT/SGPT, AST/SGOT, ALP, total bilirubin, LDH, creatinine, BUN or Urea (as per site-specific clinical practice; see [Appendix F](#) to convert Urea to BUN), glucose, Na, K, Ca, Cl, Mg, albumin, eGFR determination (according with the Mayo Clinic Quadratic Equation);
- ECG, QTc determination (according with Bazett's correction formula);
- Haematology: RBC count, HCT, Hb, MCV, MCH, MCHC, WBC count (full and differential), PLT count;
- Spleen evaluation by MRI or CT scan;
- Collection of a blood sample for the quantitative RT-PCR evaluation of JAK2^{V617F} mutational status on peripheral blood (PB) granulocyte;

- Assessment of disease-related symptoms using the MPN-SAF QOL Questionnaire [24, 32];
- Bone marrow histological evaluation (only for cycle 6) in patients who have consented to this optional exploratory research and that have not any medical contraindication to bone marrow sampling as judged by the Investigator;
- Therapeutic response evaluation according to the clinico-haematological ELN response criteria [21] (see [paragraph 4.6.1](#));
- Therapeutic response evaluation according to the “new” ELN criteria (i.e. **revised** ELN response criteria) [33] (see [paragraph 4.8.7](#)) (only for cycle 6);
- **Only for Cycle 3:** Givinostat administration;
- Used/unused/partially used Givinostat supply return and Givinostat accountability.

All phlebotomies performed in the first 3 weeks of treatment will be **not** counted to assess the therapeutic response.

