4.8.7 Evaluation of preliminary efficacy according to the revised ELN criteria

Disease response will be evaluated also according to the following “**new**” ELN criteria (i.e. the **revised** ELN response criteria) **after 6 cycles** of treatment with Givinostat in **Part B** [33].

- **Complete remission:**
 1. *Durable* resolution of disease-related signs including palpable hepatosplenomegaly improvement, and *large symptoms improvement*, **and**
 2. *Durable* peripheral blood count remission, defined as HCT < 45% without phlebotomies, and PLT count $\leq 400 \times 10^9/L$, and WBC count < $10 \times 10^9/L$, **and**
 3. No progressive disease, and absence of any hemorrhagic or thrombotic event, **and**
 4. Bone marrow histological remission defined as the presence of age-adjusted normo-cellularity, and disappearance of tri-linear hyperplasia, and absence of grade > 1 reticulin fibrosis.
- **Partial remission:**
 1. *Durable* resolution of disease-related signs including palpable hepatosplenomegaly, and *large symptoms improvement*, **and**
 2. *Durable* peripheral blood count remission, defined as HCT < 45% without phlebotomies, and PLT count $\leq 400 \times 10^9/L$, and WBC count < $10 \times 10^9/L$, **and**
 3. No progressive disease, and absence of any hemorrhagic or thrombotic event, **and**
 4. No bone marrow histological remission defined as persistence of tri-linear hyperplasia.
- **No response:** any response that does not satisfy partial remission.
- **Progressive Disease:** transformation into post-PV myelofibrosis, myelodysplastic syndrome or acute leukemia (according to the IWG-MRT criteria for the diagnosis of post-PV myelofibrosis and according to WHO criteria for the diagnosis of myelodysplastic syndrome and acute leukemia).

Please note that according to the “new” ELN criteria (i.e. **revised** ELN response criteria) [33]:

- 1) Molecular response is not required for assignment as Complete Remission or Partial Remission. Molecular response evaluation requires analysis in peripheral blood granulocytes. Complete response is defined as eradication of a pre-existing abnormality. Partial response applies only to patients with at least 20% mutant allele burden at baseline. Partial response is defined as $\geq 50\%$ decrease in allele burden.
- 2) “*Durable*” is defined as lasting at least 12 weeks.
- 3) “*Large symptom improvement*” is defined as ≥ 10 points of decrease in MPN-SAF Total Symptom Score [32].

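### Patients who refuse marrow sampling are dropped even from the revised-ELN parameters that need no marrow, which does not match the analysis sets named in 6.2.7.1

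*Protocol*

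**What the plan says.** Protocol 4.5.4.2.1 schedules the Part B marrow examination "in patients who have consented to this optional exploratory research". A patient who declines may still enter Part B, but "this patient will not be counted to assess the related exploratory endpoints". The bracket that follows names two endpoints: the overall revised-ELN response rate after 6 cycles, and "the evaluation of the effect of Givinostat on each single response parameter according to the revised ELN response criteria". Section 4.5.3.6 and footnote A of the Part B flow-chart in Appendix A repeat the rule.

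Section 4.8.7 builds the revised-ELN response from four criteria:

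- Criterion 1 asks for durable "resolution of disease-related signs including palpable hepatosplenomegaly", together with a large symptom improvement, which means at least 10 "points of decrease in MPN-SAF Total Symptom Score".
- Criterion 2 is durable "peripheral blood count remission, defined as HCT < 45% without phlebotomies, and PLT count" and WBC limits.
- Criterion 3 is no progression and no haemorrhagic or thrombotic event.
- Criterion 4 is the marrow. For complete remission it is "Bone marrow histological remission defined as the presence of age-adjusted normo-cellularity", with further histological conditions. For partial remission it is "No bone marrow histological remission defined as persistence of tri-linear hyperplasia".

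Section 6.2.7.1 lists the same two revised-ELN endpoints for Part B and bases them on ITT and PP. It mentions no marrow consent. Section 6.2.1 likewise puts all efficacy analyses on ITT.

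**The concern.** The exclusion is wider than its reason. A missing marrow makes criterion 4 unassessable. It does not affect a blood count, a symptom score, palpation of spleen and liver, or a record of thrombotic and haemorrhagic events. Yet the rule removes the refuser from each of those parameters too.

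Two things are at stake. First, Part B has at most 28 patients, and section 6.2 gives estimation with adequate precision as the main purpose of the study, so each patient left out is felt. Second, the non-marrow parameters would describe only the patients who accepted an optional invasive test. There is also a drafting problem: the visit sections define a consent-based set and the statistical section names ITT and PP, and nothing says which governs.

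**Working it through.** **What each parameter needs, and who has it.** The schedules are in 4.5.4.2.1 and 4.5.4.2.3 to 4.5.4.2.5.

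| Revised-ELN element (4.8.7) | Source | Scheduled regardless of marrow consent? |
|---|---|---|
| Palpable organomegaly | Physical examination | Yes |
| Symptom-score fall of at least 10 points | MPN-SAF at screening, Cycles 3 and 6 | Yes |
| Durable HCT, PLT and WBC remission | Haematology at screening and each Day 28; phlebotomy record | Yes |
| Progression, haemorrhagic or thrombotic events | Visit and adverse event records | Yes; 4.8.7 does not tie this to the optional sample |
| Marrow histology | Optional sample | No |
| Complete or partial remission | All four criteria | No, since criterion 4 is part of both |

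Only the last two rows depend on consent.

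**The plan's own figures.** The protocol gives no precision target or refusal rate for the revised-ELN endpoints. Its only design figures are for the primary endpoint (6.3): 12 patients then 28, stop at 6 or fewer responses, reject the null at 18 or more, rates 0.50 and 0.75. Exact binomial enumeration gives early termination 0.613, expected size 12 + (1 − 0.613) × 16 = 18.2, type I error 0.081 and power 0.902. All match the protocol. Nothing in this point touches them.

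**Precision.** Inputs are a maximum of 28 patients (6.3), two-sided 95% intervals (6.2), an assumed observed rate of 50% and an assumed refusal share f. The analysed number is n = 28 × (1 − f), rounded. The interval is Clopper–Pearson, and the standard error inflates by √(28/n).

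| f (assumed) | n | Observed | Exact 95% CI | Half-width (points) | SE inflation |
|---|---|---|---|---|---|
| 0% | 28 | 14/28 | 30.6–69.4% | 19.4 | 1.00 |
| 20% | 22 | 11/22 | 28.2–71.8% | 21.8 | 1.13 |
| 30% | 20 | 10/20 | 27.2–72.8% | 22.8 | 1.18 |
| 50% | 14 | 7/14 | 23.0–77.0% | 27.0 | 1.41 |

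Keeping refusers in the non-marrow parameters returns each of these rows to the first.

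**Selection.** Let the true rates be p_c in consenters and p_r in refusers. The consenter-only rate differs from the all-patient rate by p_c − [(1 − f)p_c + f·p_r] = f(p_c − p_r). For an assumed difference of 10 to 30 points, this is 1 to 3 points at f = 10%, 2.5 to 7.5 at f = 25% and 5 to 15 at f = 50%. The documents give neither f nor the sign of the difference.

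**The case against.** The strongest defence is that these endpoints are exploratory and descriptive, and that one common denominator lets the single parameters be reconciled with the composite they build. That is a real advantage, and the fix gives some of it up. It does not explain why the visit sections and 6.2.7.1 disagree.

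A reader might infer that refusers' data are collected and then thrown away. The documents do not support this. Section 6.2.7.1 still analyses every Part B patient's HCT, platelets, WBC, spleen size and symptoms under the clinico-haematological ELN single parameters, the spleen endpoint and MPN-SAF. What refusers lose is the revised-ELN versions: 12-week durability, the 10-point symptom-score fall, palpable organomegaly, and progression or events.

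A reader might also infer that refusers should count in the overall revised-ELN rate, because criteria 1 to 3 are nearly the same in both categories. They should not. Criterion 4 belongs to complete and to partial remission, and a marrow can satisfy neither version, for example with hyperplasia gone but fibrosis above grade 1. Meeting criteria 1 to 3 is therefore not the same as a revised-ELN response.

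Finally, selection bias is not shown. Consent to the baseline marrow is sought before treatment, so that refusal cannot be driven by outcome, and 6.2.1 already asks for a table and listing of reasons for exclusion from the analysis populations. What stands is a possible effect of unknown direction.

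**Conclusion.** The point holds in a narrow form and is minor. The exclusion is justified for criterion 4 and for the complete/partial remission rate. It is not justified for the non-marrow revised-ELN parameters, and it does not match 6.2.7.1. One could read the consent rule as a restriction inside ITT and PP, but the protocol does not say so.

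Lost precision is certain for any refusal above zero; its size is not known. At an assumed 50% rate, the half-width goes from 19.4 points to 21.8 at 20% refusal and 27.0 at 50%. The starting number of 28 is a maximum. Part A patients at the MTD may count towards Stage 1 (6.3), six were treated at that dose (Amendment 2 rationale), and the marrow examination and Total Symptom Score are specified only for Part B, so the revised-ELN denominator could start nearer 28 − 6 = 22. A Stage 1 stop would leave at most 12. The primary response rate, its error rates and the futility rule are unaffected.

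**What to change.** In 4.5.3.6, 4.5.4.2.1 and Appendix A footnote A, limit the exclusion to criterion 4 and the complete/partial remission assignment. Changing only some of the three would create a new contradiction. Analyse the non-marrow revised-ELN parameters in the ITT set, as 6.2.7.1 already states, with consenter-only results alongside so that they can be reconciled with the composite. Report the number of refusers.

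A rate of patients meeting criteria 1 to 3 may be shown if it is labelled as a supplementary measure and not as the revised-ELN response. The same edit could say how patients with a medical contraindication to sampling are handled: they also lack a marrow result, but the rule mentions only refusal.

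The cost is a sentence in each of three places, with no new visit, procedure or patient. The downside is that denominators will differ between the single parameters and the composite, so each table should state its n.

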4.3.3.2.2 Dose increase for inadequate efficacy in **Part B**

In **Part B**, the initial dose of Givinostat will be the MTD defined in **Part A** (i.e. 100 mg b.i.d.).

Based on evaluations performed as part of the visit procedures of the Day 28 of each Cycle up to the Cycle 5 (i.e. Cycle 1 Day 28, Cycle 2 Day 28, Cycle 3 Day 28, Cycle 4 Day 28, Cycle 5 Day 28) and/or in any necessary additional study visit, the Givinostat doses have to be decreased in case of the occurrence specific toxicities (see [paragraph 4.3.3.2.1](#)).

After a dose reduction, dosing may be restarted and then increased following recovery of the observed toxicity(ies) to controlled levels. The objective for restarting and then escalating after a reduction for safety reasons is to find the highest safe dose regimen of Givinostat for each patient that is necessary to obtain a clinico-haematological response, with increase in dose not more than the MTD defined in **Part A** (i.e. 100 mg b.i.d.).

After a dose reduction and in order to optimize the response for each individual patient avoiding specific drug-related toxicities, the Givinostat dosage **may be increased** for patients who meet all the following criteria, based on evaluations performed as part of the visit procedures of the Day 28 of each Cycle up to the Cycle 5 (i.e. Cycle 1 Day 28, Cycle 2 Day 28, Cycle 3 Day 28, Cycle 4 Day 28, Cycle 5 Day 28):

1. Inadequate efficacy as demonstrated by one or more of the following points:
 - a) HCT $\geq 45\%$, **or** HCT $< 45\%$ but at least 1 phlebotomy performed after the first 3 weeks of treatment, **or** HCT $< 45\%$ but at least three point higher than the HCT obtained at baseline (i.e. HCT at baseline (in %) plus at least a value of 3%), **or**
 - b) WBCs count $> 10 \times 10^9/L$, **or**
 - c) PLTs count $> 400 \times 10^9/L$, **and**

2. PLTs count > local LLN, **and**
3. Hb value \geq 12 g/dL, **and**
4. ANC \geq 1.5 x 10⁹/L.

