6.2.7 Exploratory evaluations

6.2.7.1 Parts A and B

The following exploratory parameters will be evaluated using ad-hoc descriptive analysis in **Parts A** and **B** based on ITT and PP:

- The effect of Givinostat on each single response parameter according to the clinico-haematological ELN (for PV and ET) [21] (see [paragraph 4.6.1](#)) and EUMNET response criteria (for MF); note that only in case the enrolment in **Part A** is slow (i.e. **< 5 patients enrolled in 3 months**, the eligibility for this part of the study may be expanded to all patients with cMPN).
- Effects of Givinostat on PD markers.
- Effects of Givinostat on spleen size in patients with confirmed splenomegaly at baseline.
- Improvement of constitutional symptoms evaluated according to MPN-SAF QOL questionnaire [24, 32].
- Reduction of the JAK2^{V617F} allele burden, tested by quantitative RT-PCR.
- Reduction of the symptomatic treatment of pruritus in term of dosage and/or days of treatment.

The following exploratory parameters will be evaluated using ad-hoc descriptive analysis in **Part B** based on ITT and PP:

- The preliminary efficacy of Givinostat **after 6 cycles** of treatment according to the “new” ELN criteria (i.e. **revised** ELN response criteria) [33] (see [paragraph 4.8.7](#)).
- The effect of Givinostat on single parameters of the “new” ELN criteria (i.e. **revised** ELN response criteria) [33] (see [paragraph 4.8.7](#)).

Explorative endpoints will be summarized by descriptive methods. Default summary statistics and changes from baseline (where applicable) to each time point for all parameters will be produced.

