6.2.8 Other Safety evaluation

All patients who receive at least one dose will be included in the safety evaluation. Safety data including laboratory evaluations, physical exams, ECG monitoring and vital signs assessments will be summarized at each time point. Descriptive statistics

(arithmetic mean, standard deviation, median, minimum and maximum) will be calculated for quantitative safety data as well as for the difference from baseline, if applicable. Frequency counts will be compiled for classification of qualitative safety data. In addition, a shift table describing out of normal range shifts (low/normal/high values) will be provided for clinical laboratory results. A normal-abnormal shift table will also be presented for physical exam and ECG results.

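### Part B schedules no blood count between the mandatory pre-treatment phlebotomy and the first dose, so HCT, Hb and RBC changes from baseline mix phlebotomy with drug effect in patients entering at HCT ≥45%

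*Protocol*

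**What the plan says.** Part B pre-treatment visit (Protocol 4.5.4.2.1). The procedures include "Haematology: RBC count, HCT, Hb, MCV, MCH, MCHC, WBC count (full and differential), PLT count". On timing: "Pre-treatment evaluations must be performed up to 4 weeks before the treatment start within" a margin of 7 days either way. The same section then orders the phlebotomy: "After the check that all eligibility criteria are met by the patient and in any case before the treatment start", patients with HCT of 45% or more "have to perform phlebotomy(ies) to normalize the HCT value" to under 45%.

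Day 1 of Cycle 1 (Protocol 4.5.4.2.2). The list opens with "The following procedures must be performed exactly at Day 1 of Cycle 1 of" Part B. It contains adverse events, concomitant medication, non-drug therapies, PD and PK samples, and the first dose. It contains no blood count. The Part B flow-chart (10.1.2) agrees: the haematology row is empty in both Day 1 columns. The next scheduled count is at Day 28 of Cycle 1 (4.5.4.2.3).

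Planned analyses. Section 6.2.7.1 covers each single ELN response parameter, HCT among them, and states: "Default summary statistics and changes from baseline (where applicable) to each time point for all parameters will be produced". For laboratory safety data, Section 6.2.8 says descriptive statistics "will be calculated for quantitative safety data as well as for the difference from baseline, if applicable".

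Dose-increase rule (4.3.3.2.2 and Table 4). One of its alternative signs of inadequate efficacy is an HCT below 45% that is nevertheless "at least three point higher than the HCT obtained at baseline".

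**The concern.** A change from baseline is useful only if the baseline describes the patient at the start of treatment. Here the only scheduled pre-dose HCT precedes a protocol-mandated intervention that lowers HCT. For anyone entering at 45% or more, the recorded baseline is a value the patient should no longer have when dosing begins. Hb and RBC fall with the same phlebotomy and carry the same artefact into the safety summaries.

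The study has a single arm, so no control group can subtract this component. At stake is the reading of the exploratory HCT effect and of the Hb and RBC safety shifts: a reader could not tell whether HCT fell, held or drifted upward on treatment.

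**Working it through.** **1. The plan's own figure, as background.** Section 6.3 stops at 6 or fewer responders of 12 and rejects the null at 18 or more of 28, with rates 0.50 and 0.75. Exact binomial calculation gives:
- early termination under the null: P(X ≤ 6 | 12, 0.50) = 0.6128 (stated 0.613);
- expected size: 12 + (1 − 0.6128) × 16 = 18.20 (stated 18.2);
- type I error 0.0815 before rounding to the stated precision (0.08148; stated 0.081);
- power 0.9017 (stated 0.902).

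All four agree. None uses a change from baseline; response under 4.6.1 rests on HCT below 45% without phlebotomy, an absolute threshold.

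**2. Order of events for a Part B patient entering at HCT ≥45%.** Screening count, eligibility check, phlebotomy to below 45%, first dose, next scheduled count at Day 28 of Cycle 1. No scheduled HCT lies between the phlebotomy and the first dose.

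**3. What the change from screening contains.** Let S be the screening HCT, P the HCT after phlebotomy and H the HCT at a later visit. Then

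H − S = (P − S) + (H − P).

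The first term is the phlebotomy fall. It is negative by mandate whenever S ≥ 45, since P < 45. The second term is the on-treatment change: drug effect, natural course and any further phlebotomy. P is not scheduled, so the two terms cannot be separated.

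**4. Size.** The protocol gives no distribution of S or P, so the values below are assumptions. The table shows P − S in HCT points, which is the whole change if HCT then stays at P.

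| Screening S | P = 44.9 | P = 43 | P = 42 |
|---|---|---|---|
| 45 | −0.1 | −2 | −3 |
| 47 | −2.1 | −4 | −5 |
| 50 | −5.1 | −7 | −8 |
| 53 | −8.1 | −10 | −11 |

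For S = 50, any P below 45 gives a change beyond −5. The sign can also mislead: with S = 50, P = 43 and a rise on treatment to 44.9, the change from screening is 44.9 − 50 = −5.1, while the change from the post-phlebotomy value is 44.9 − 43 = +1.9.

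The shift in the group mean is the share of affected patients times their mean fall. For an assumed fall of 5 points it is −1.25 at a 25% share, −2.5 at 50% and −5 at 100%.

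**5. The dose-increase limb.** With baseline b, it requires HCT < 45 and HCT ≥ b + 3 together. That needs b + 3 < 45, so b < 42. At b = 45 it would need HCT ≥ 48 and < 45 at once. On a screening value of 45% or more the limb can never be met; on any baseline from 42% upward it cannot be met either.

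**The case against.** Several counter-arguments have force.

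- **The effect is not phlebotomy alone.** A reader might infer that the HCT change measures the phlebotomy and not the drug. The documents do not support that. The change contains both, and only in patients entering at 45% or more. Inclusion criterion 5a also admits patients below 45% who need phlebotomy, and they fall outside the mandate.
- **The primary endpoint.** A reader might infer that the Simon test is biased. It is not biased through change from baseline, because response uses an absolute threshold. Affected patients do start treatment already below 45%, but that is a feature of the endpoint which a Day 1 count would not alter; only phlebotomies in the first 3 weeks are disregarded.
- **The dose-increase rule.** A reader might infer that the limb makes sense only with a post-phlebotomy baseline, or that the rule cannot work. Neither follows. A patient entering below 42% can meet the limb on an ordinary screening value. A post-phlebotomy value of 42% to 44.9% would still fail it. It is also one alternative among several, including HCT ≥45%, a phlebotomy after week 3, WBC and platelets. What stands is that the protocol does not say which HCT is meant.
- **The size depends on what HCT does next.** In uncontrolled disease without drug effect, HCT may climb back, and the change from screening would shrink. The 5-point example therefore assumes that HCT stays below 45%.
- **Baseline is often defined in an SAP, and sites may recheck HCT.** Both are fair. Screening may take more than one visit, and confirming HCT below 45% implies a measurement. But no such value is required, and a definition such as last value before first dose works only where one was recorded.

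**Conclusion.** The point holds in a limited form. In Part B no haematology is scheduled between the mandated phlebotomy and the first dose. For patients entering at HCT ≥45%, the planned HCT change (6.2.7) and the Hb and RBC differences (6.2.8) include a non-drug fall that the scheduled data cannot isolate. Over the assumed values above, that fall is 0.1 to 11 HCT points per affected patient; its effect on group means depends on a share the protocol does not state. The conclusion rests on the screening value serving as baseline where no later pre-dose count happens to exist.

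The consequence is confined to exploratory and safety summaries. It gives no reason to doubt the sample size or the primary test. It is still worth correcting before enrolment, because a missed pre-dose value cannot be recovered later.

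The baseline-referenced limb of the dose-increase rule is a separate matter of unclear reference. It cannot be met at a baseline of 42% or more.

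**What to change.** - Add haematology to the Part B Day 1 pre-dose blood draw, after any pre-treatment phlebotomy, in Section 4.5.4.2.2 and the flow-chart in 10.1.2.
- For the analyses in 6.2.7 and 6.2.8, define the baseline for HCT, Hb and RBC as the last post-phlebotomy, pre-dose value, and report the screening value alongside it.
- Ask the sponsor to reconcile Section 4.3.3.2.2 and Table 4 with the visit schedule and to state which HCT the word baseline means there. No dosing criterion is proposed here.

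Cost: one tube at a draw already made for PD and PK, analysed locally, for about 28 patients, plus one definition. The sample size and decision rules do not change.
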